6.3.3 Withdrawal of patients from treatment or study

6.3.3.1 Withdrawal from treatment

A patient should be withdrawn from the study treatment if, in the opinion of the investigator, it is medically necessary, or if it is the wish of the patient. Specific treatment stopping criteria are provided in Section 6.4.7.

When a patient is withdrawn from treatment, the study site must immediately notify the study medical monitor, and the date of last IMP dose and the date and reason for treatment withdrawal should be clearly described in the relevant sections of the eCRF. If a patient is removed from treatment because of an AE, the reason for treatment withdrawal should always be stated as 'adverse event' irrespective of whether this was the investigator's or the patient's decision.

The patient will continue to participate in the study without taking study treatment. Patients who stop study treatment prior to the exit visit should undergo all follow-up visits and procedures through study completion, unless they are unwilling or unable or consent has been withdrawn. Patients who wish to fully withdraw from the study before completion should be encouraged to complete the Early termination visit (see Table 2).

6.3.3.2 Withdrawal from study

A patient may withdraw from the study at any time at his/her own request or at the request of their legally authorized representative, or may be withdrawn at any time at the discretion of the investigator for safety, behavioral, compliance, or administrative reasons. This is expected to be uncommon. Whenever possible and irrespective of the reason for withdrawal, the patient should be examined as soon as possible. Relevant samples should be obtained and all relevant assessments should be completed. The eCRF should be completed as far as possible. Date and reason for the study withdrawal should be clearly described in the eCRF.

Once a patient leaves the study, he/she may not reenter the study.

6.3.3.3 Lost to follow-up

A minimum of 3 documented attempts must be made to contact any patient lost to follow-up at any point prior to the last scheduled contact (office visit or telephone contact). At least 1 of these documented attempts must include a written communication sent to the patient's last known address via courier or mail (with an acknowledgment of receipt request) asking that the patient return to the site for final safety evaluations and to return any IMP.

Should the patient continue to be unreachable, they will be considered to have withdrawn from the study.

6.3.4 Replacement of withdrawn patients

Withdrawn patients will not be replaced.

6.3.5 Specific restrictions/requirements

6.3.5.1 Acceptable methods of contraception

Acceptable methods of contraception include:

- Combined (estrogen- and progestogen-containing) hormonal contraception associated with inhibition of ovulation:
 - Oral, intravaginal or transdermal.
- Progestogen-only hormonal contraception associated with inhibition of ovulation:
 - Oral, injectable or implantable.
- Intrauterine device.
- Intrauterine hormone-releasing system.
- Bilateral tubal occlusion.
- Vasectomized partner (provided that the partner is the sole sexual partner of the WOCBP study patient and the vasectomized partner has received medical assessment of the surgical success).
- Sexual abstinence (defined as refraining from heterosexual intercourse during the entire period of risk associated with study treatments).
- Male condom, with or without spermicide (for male study patients with female partners of childbearing potential only).

Not all methods of contraception may be available in all of the countries in which the study is being conducted.

Note: Sexual abstinence is accepted only when it is the preferred and usual lifestyle of the patient.

Patients must agree to use an acceptable method of contraception during the study and for 8 weeks after their last dose of IMP.

Male patients will be counseled to avoid donating semen during the time between the first screening and the final exit visit and for the 8 weeks after their last dose of IMP.

6.3.5.2 Vaccination and preventive antibiotic requirements

Details about required vaccination against *N. meningitidis* (Types A, C, W, Y, and B), *S. pneumoniae* (with a PCV13 or PPSV23 vaccine), and *H. influenzae* Type B (Hib) and required/recommended preventive antibiotics are provided in Section 6.4.1.2.

6.3.6 Study stopping criteria

The study enrollment will be suspended if:

- 2 patients from 2 different investigational sites experience a Grade 4 AE assessed as related to the IMP by the investigator.

- 1 patient experiences a Grade 5 AE assessed as related to the IMP by the investigator.

The sponsor will thoroughly evaluate the reported adverse reactions and will resume the study only if an alternative explanation of the reported events is identified. In case the decision to stop the study is made, the sponsor will communicate the appropriate action for enrolled patients who are on treatment with the active drug based on the risk-benefit assessment. The sponsor or designee will also promptly inform the relevant regulatory authorities of the suspension/termination along with the reasons for such action, when applicable. Where required by applicable regulations, the investigator or head of the medical institution must inform the IRB/IEC.

The sponsor reserves the right to close the study site or terminate the study at any time for any reason at the sole discretion of the sponsor.

Unjustifiable risk and/or toxicity or substantial changes in risk-benefit considerations, which could raise medical and/or ethical reasons affecting the continued performance of the study, may cause premature termination of the clinical study or one of the study parts.

The following criteria may cause premature termination of a study site:

- Favorable opinion withdrawn by the IRB/IEC or local health authorities.
- Failure of the investigator to comply with the protocol, the requirements of the IRB/IEC or local health authorities, the sponsor's procedures, or GCP guidelines
- Inadequate or no recruitment (evaluated after a reasonable amount of time) of participants by the investigator.
- Withdrawal of the license to manufacture and/or of the permission to import.

If the study is prematurely terminated or suspended, the sponsor shall promptly inform the investigators, the IECs/IRBs, the regulatory authorities, and any contract research organization(s) used in the study of the reason for termination or suspension, as specified by the applicable regulatory requirements. The investigator shall promptly inform the participant and should assure appropriate participant therapy and/or follow-up.

6.4 Treatments

6.4.1 Treatments administered

6.4.1.1 Investigational medicinal products

Table 3 Investigational medicinal products

Investigational product	Dosage form	Route	Dose	Dosage regimen
Pegcetacoplan	Sterile solution in stoppered glass vials	Subcutaneous	1080 mg	Twice weekly
Placebo	Sterile solution in stoppered glass vials	Subcutaneous	Not applicable	Twice weekly

The pegcetacoplan treatment group will receive a dosage of 1080 mg twice weekly via s.c. infusion (20 mL) during the double-blind treatment period (24 weeks).

The placebo group will receive placebo s.c. infusion twice weekly during the double-blind treatment period.

Following the double-blind treatment period, patients from both treatment groups may enter the open-label treatment period (24 weeks) and will receive pegcetacoplan 1080 mg twice weekly via s.c. infusion (20 mL) (equivalent to 308 mg/day).

The open-label treatment period will be followed by an open-label maintenance period (maximum of additional 48 weeks or until the product becomes commercially available, whichever occurs first), and patients who benefited from therapy without significant side effects during the double-blind treatment period will continue receiving pegcetacoplan 1080 mg twice weekly via s.c. infusion (20 mL).

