6.1.3 Open-label treatment period (24 weeks): Part B

All patients who complete the 24-week double-blind treatment period will be eligible to enter the open-label treatment period, in which they will receive pegcetacoplan 1080 mg twice weekly for up to 24 weeks (Week 48).

6.1.4 Open-label maintenance period (up to additional maximum 48 weeks or until the product becomes commercially available): Part C

After completion of the open-label treatment period, patients who benefit from therapy without significant side effects will continue receiving pegcetacoplan 1080 mg s.c. twice weekly for a maximum of 48 additional weeks or until the product is commercially available, whichever occurs first. In the event that the commercial product is not yet available at the end of Part C, patients will be managed outside of the current study on a case-by-case basis, in accordance with applicable laws and regulations.

At the end of the study, the sponsor will inform the investigators of the appropriate course of action based on the study results.

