6.4.3 Method of assigning patients to treatment groups

Randomization will occur through the IRT system.

All patients who meet all the inclusion criteria and none of the exclusion criteria will be enrolled in the study after eligibility review by the study medical monitor, until such time that 57 patients have been enrolled in the study. Patients will then be randomly assigned through the IRT system to either pegcetacoplan or placebo in a 2:1 ratio. The randomization will be stratified according to number of transfusions during the 6-month period prior to randomization ≥ 1 ; 0. Every effort should be made to enroll patients in both subgroups.

Blinded IMP supplies labeled with kit numbers and other information as per Master Label and in line with regulatory requirements will be provided to each study site. IMP dosing will be initiated at the site after randomization. At each visit when IMP is administered and dispensed, the study staff will contact the IRT to obtain appropriate kit numbers.

For the open-label treatment and maintenance periods, all patients will receive pegcetacoplan open-label.

Please refer to the study manuals for further details of randomization and unblinding.

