6.4.7 Treatment stopping criteria

Pegcetacoplan will be discontinued in an individual patient if any of the following laboratory abnormalities and/or AEs are observed that are assessed as causally related to the IMP (i.e., no alternative explanation is identified) by the investigator:

- Any Grade ≥ 3 nonhematological laboratory abnormality (other than Grade 3 hypoglycemia; Grade 3 AST, GGT, and total bilirubin caused by unconjugated bilirubin elevation).

- Grade 4 thrombocytopenia for \geq 7 days, or Grade \geq 3 thrombocytopenia associated with bleeding.
- Grade 4 neutropenia for \geq 7 days, or Grade \geq 3 neutropenia associated with infection.
- Febrile neutropenia of any grade.
- Any Grade \geq 3 nonhematological toxicity (other than Grade 3 nausea, vomiting, or diarrhea \leq 72 hours in duration with adequate prophylactic and supportive care).
- A severe hypersensitivity reaction (including anaphylaxis): the IMP must immediately be permanently discontinued and appropriate treatment instituted.

The use of prohibited medications (Section 6.4.10.2) during the study will require the patient to be permanently discontinued from the study treatment. Study treatment must also be discontinued if a female patient becomes pregnant.

Procedures in case of withdrawal from study treatment are provided in Section 6.3.3.1.

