6.4.9 Blinding and unblinding

6.4.9.1 IMP blinding

Active and placebo product will be of identical appearance.

The IMP blind will be maintained through the Week 24 primary endpoint analysis. Patients, the sponsor, investigators, CROs and all study site personnel involved with the study, carrying out study procedures, evaluating patients, entering study data, and/or evaluating study data will remain blinded to treatment allocations until all patients have completed the Week 24 assessments and the database has been locked for the analysis at Week 24.

Certain laboratory data could potentially hint at the possibility that the patient is on active treatment; however, these also represent safety parameters and, therefore, investigators will not be blinded to hematology and safety laboratory results. Both sponsor and investigators will be blinded through the Week 24 primary endpoint analysis for the following laboratory parameters: anti-pegcetacoplan peptide and anti-PEG antibodies, complement profile, pegcetacoplan concentrations and PK parameters.

After Week 24, all patients will receive open-label pegcetacoplan.

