9.4 Protocol deviations

A protocol deviation is generally an unplanned excursion from the protocol that is not implemented or intended as a systematic change. The investigator is responsible for ensuring the study is conducted in accordance with the procedures and evaluations described in this protocol and must protect the rights, safety, and welfare of patients. The investigator should not implement any deviation from, or changes to, the protocol, unless it is necessary to eliminate an immediate hazard to study patients.

A protocol waiver is a documented prospective approval of a request from an investigator to deviate from the protocol. Protocol waivers are strictly prohibited.

When a deviation from the protocol is identified, the investigator or designee must ensure that the study medical monitor is notified. The study medical monitor will follow up with the investigator, as applicable, to assess the deviation and the possible impact to the safety and/or efficacy of the patient to determine patient continuation in the study.

The investigator and CRO must contact Sobi immediately if a deviation is discovered that significantly affects or has the potential to significantly affect human subject protection or the reliability of study results.

The investigator will also assure that deviations are reported and documented in accordance with IEC/IRB and applicable regulatory requirements.

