## **11 APPENDICES**

### **11.1 CHANGES TO THE PROTOCOL SPECIFIED ANALYSES**

In the event that there are discrepancies between the protocol and the SAP, the SAP will take precedence.

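### Section 6.4.1.1 ties Part C continuation to benefit in the double-blind period, when the placebo arm gets only placebo; section 6.1.4 and the synopsis apply the condition after Part B

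*Protocol*

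**What the plan says.** The continuation rule for Part C appears in three places in the protocol.

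- **Section 6.4.1.1**, after describing the maintenance period that follows Part B: "patients who benefited from therapy without significant side effects during the double-blind treatment period will continue receiving pegcetacoplan".
- **Section 6.1.4** and the **synopsis**, in the same words: "After completion of the open-label treatment period, patients who benefit from therapy without significant side effects will continue receiving pegcetacoplan".

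On what each arm receives in Part A, section 6.4.1.1 itself says: "The placebo group will receive placebo s.c. infusion twice weekly during the double-blind treatment period". It then says that both groups may enter Part B and receive open-label pegcetacoplan there.

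Section 6.4.3 names the drug for the later periods and sets no condition for continuing: "For the open-label treatment and maintenance periods, all patients will receive pegcetacoplan open-label". SAP section 2.2 lists Part C by its maximum length and commercial availability, and it too gives no benefit condition.

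**The concern.** The sentence in 6.4.1.1 decides who goes on receiving drug after Week 48, and it refers to the wrong period. A placebo-randomized patient cannot show benefit from pegcetacoplan before Part B. A site applying 6.4.1.1 as written could therefore stop pegcetacoplan at Week 48 in a patient who first responded on open-label drug.

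The same sentence misjudges the other arm. A pegcetacoplan patient who did well in Part A but lost benefit in Part B would still meet it.

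What is at stake is access to treatment in Part C and, through that, which patients contribute to the descriptive Week 96 data.

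**Working it through.** No figure in the plan depends on this point, so the check is mainly a comparison of text.

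**1. The three statements side by side**

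| Place | When benefit is judged | Drug the placebo arm has had by then |
|---|---|---|
| 6.4.1.1 | During the double-blind period (Part A) | Placebo only |
| 6.1.4 | After Part B is complete, present tense | 24 weeks of open-label pegcetacoplan |
| Synopsis | After Part B is complete, present tense | 24 weeks of open-label pegcetacoplan |

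Section 6.1.4 and the synopsis do not name a window over which benefit is assessed. They do place the condition after Part B and make it a matter of current benefit. Section 6.4.1.1 places it in Part A. The two rules differ for any patient whose status changes between the periods, and for the placebo arm the treatment itself changes between them.

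**2. Does other text show which is meant?** Yes.

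- Protocol 4.2 and 6.2 describe open-label treatment offered to all enrolled patients, followed by a further 48 weeks for continuity of treatment.
- Protocol 8.3.4.4 and SAP 7.5 present the Part C efficacy data by the arm randomized in Part A and combined. That layout presupposes placebo-randomized patients in Part C.

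These passages support the rule in 6.1.4. None of them restates the benefit condition or corrects the sentence in 6.4.1.1.

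**3. Does any rule formally override 6.4.1.1?** No.

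- SAP 11.1 says: "In the event that there are discrepancies between the protocol and the SAP, the SAP will take precedence". That ranks the SAP above the protocol, but the SAP has no continuation criterion to put in place of this one.
- Protocol 6.4.7 begins: "Pegcetacoplan will be discontinued in an individual patient if any of the following laboratory abnormalities and/or AEs are observed". Its criteria are not confined to Part A, so they limit the risk of continuing a patient with serious drug-related toxicity. They do not cover absence of benefit.

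**4. Size**

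- Planned enrollment is 57 with 2:1 allocation, so the placebo arm is 57 × 1/3 = 19. This is a planned ceiling, not an estimate. SAP 1.1 says enrollment ended before the target, the actual number is not given, and benefit is not defined.
- SAP 1.1 allows treatment until 10 July 2024. Week 48 is Day 337 and Week 96 is Day 673 (protocol Table 2). On target days, reaching Week 48 by then needs a first dose no later than 10 July 2024 − 336 days = 9 August 2023. A full Part C needs one no later than 10 July 2024 − 672 days = 7 September 2022. Early termination therefore shortens or removes Part C for everyone dosed after those dates. The documents give no first-dose dates, so the arithmetic goes no further.

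**The case against.** The strongest reply is that this is a slip of the pen which no sensible site would follow. Every other relevant statement fits Part C access for former placebo patients. Neither version of the rule says that only the described group may continue, so treating a Part B responder under 6.1.4 breaches no express prohibition. Protocol 4.3 also asks sites, whenever possible, to contact the medical monitor before stopping drug. All of this is fair, and it is why the point is minor. It does not make the sentence right: a rule on access to drug names the wrong period and conflicts with two other statements of the same rule.

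A reader might infer more than the documents support:

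- **That the intent cannot be determined.** It can, from the passages listed in step 2.
- **That a site following 6.1.4 would need a forbidden waiver.** Section 9.4 does say "Protocol waivers are strictly prohibited", but it defines a waiver as advance approval of a request to depart from the protocol. Following one of the protocol's own sections is not such a request.
- **That blinded sites could not work around the error.** Under 6.4.9.1 sites "will remain blinded to treatment allocations until all patients have completed the Week 24 assessments and the database has been locked", so a Week 48 decision may come before allocation is known. The same section leaves hematology visible to investigators, who can see whether hemoglobin rose only on open-label drug. Applying 6.1.4 also needs no knowledge of allocation.
- **That patients were denied Part C.** Nothing in either document shows this.

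**Conclusion.** The sentence in 6.4.1.1 is wrong as written: it is an internal inconsistency with 6.1.4 and the synopsis, most likely a slip for the open-label period. Severity is minor.

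The effect is confined to Part C access and descriptive Part C data. It is reduced further by early termination: under SAP 1.1, separate Part B and Part C tables are dropped, and normalization and durability are not analyzed beyond Part A. The Part A analyses, the type I error and the power are unaffected.

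The number of patients affected is unknown, with about 19 as the planned size of the placebo arm. The conclusion rests on the text alone and on no assumption about enrollment dates or response rates.

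**What to change.** In 6.4.1.1, replace the reference to the double-blind treatment period with *during the open-label treatment period (Part B)*, so that the rule agrees with 6.1.4 and the synopsis.

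If the protocol can no longer be amended, send sites a short clarification and state in the CSR which rule was applied.

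The cost is one phrase, or one site notice and one CSR sentence. No SAP change is needed, and the disposition table in SAP 6.1 already shows completion and discontinuation by study part, so no new output is required.

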6.4.1.2 Vaccination and preventive antibiotics

6.4.1.2.1 Vaccination

To receive treatment with IMP, patients will be required to be vaccinated as per ACIP recommendations for adults or children with complement deficiencies and/or immunocompromising conditions (available at <https://www.cdc.gov/vaccines/schedules/hcp/index.html>) as follows:

Patients previously vaccinated will have documented evidence of vaccination against the following within 2 years of screening: *N. meningitidis* Types A, C, W, Y, and B (administered as 2 separate vaccinations), *S. pneumoniae* (with a PCV13 or PPSV23 vaccine), and *H. influenzae* Type B (Hib) vaccine (see Section 6.3.1, Inclusion Criterion #7).

Patients not previously vaccinated will have to receive vaccines during screening as follows:

- First dose of vaccine against *N. meningitidis* Types A, C, W, and Y at least 2 weeks prior to start of study drug with second dose 2 months later (study Day 57), and then boosters every 5 years.
- First dose of the vaccine against *N. meningitidis* Type B at least 2 weeks prior to start of study drug with a second dose after at least 1 month (study Day 29). First booster dose 1 year later, and then additional booster doses every 2 to 3 years.
- *S. pneumoniae*: PCV13 and/or PPSV23 as per ACIP guidelines for adults or children with immunocompromising conditions.
- *H. influenzae* Type B: 1 dose at least 2 weeks prior to start of study drug.

Vaccination is mandatory, unless documented evidence exists that patients are nonresponders to vaccination. Documented evidence that a patient is a nonresponder to vaccination should be provided via serological result (after second dose or booster where applicable). The investigator will discuss with the sponsor regarding individual patient circumstances.

Vaccines will be sourced locally by the study sites and reimbursed by the sponsor, or sourced by the sponsor if local sourcing is not feasible.

An AxMP is a medicinal product used for the needs of a clinical study as described in the protocol, but not as an IMP. In this study, the described mandatory vaccines are considered as AxMP and safety reporting applies for them, see Sections 6.5.4.1.3.1 and 6.5.4.1.4.1.

